1. INTRODUCTION AND BACKGROUND

Infrainguinal peripheral arterial occlusive disease (PAD) is manifest over a spectrum of clinical presentations, ranging from the asymptomatic loss of peripheral pulses, leg claudication, to pain at rest, gangrene and limb-loss.¹ The magnitude of signs and symptoms is well correlated with the anatomic extent of disease.² Single-level, short arterial obstructions with moderate levels of stenosis may remain asymptomatic, while multilevel, long-segment occlusions often culminate in ischemic complications that threaten the viability of the limb.

With the advent of lower extremity angiography, definitive methods of lower extremity arterial revascularization gained popularity. Open surgical endarterectomy and bypass were employed which provided adequate channels for normalization of blood flow. When successful, symptoms of claudication and rest pain can be completely remediated and leg ulcerations will heal. Unfortunately, open surgical revascularization procedures represent significant challenges to patients with PAD, a population who often display other manifestations of systemic atherosclerosis including significant coronary artery and cerebrovascular disease. These comorbidities, amongst others, account for an undesirably high rate of morbidity and mortality following surgical revascularization, with perioperative morality rates approaching 5% in most series.³⁻⁵

On this backdrop, minimally-invasive techniques for lower extremity arterial revascularization gained a foothold. The advent of balloon angioplasty catheters (percutaneous transluminal angioplasty, or PTA) provided a percutaneous means to restore arterial flow, albeit with a trade-off between procedural morbidity and long-term durability.⁶ Metallic stents entered the armamentarium of the peripheral interventionist a decade later, first as balloon-expandable stainless steel devices but later as more flexible and crush-resistant nitinol devices, most recently with antiproliferative drug-eluting coatings to discourage in-stent restenosis.⁷⁻¹¹ Drug-eluting balloons and bioresorbable polymer scaffolds were the most recent technological additions, each developed in an effort to limit the drawbacks of metallic stents as permanently implantable foreign bodies.¹²⁻¹⁵

Atherectomy was conceived early on as another method of revascularization available for patients with PAD.¹⁶⁻¹⁹ Its value in the management of lower extremity peripheral arterial disease has been amplified in light of the difficulties associated with treating PAD with PTA alone; with or without drug-eluting devices. PTA is associated with many challenges including elastic recoil, dissection, and disruption of the internal elastic lamina.^{20,21} Because of its debulking capability, atherectomy use has helped widen the spectrum of lesions associated with PAD that are amenable to revascularization.^{21,22} Recurrent stenosis continues to be the primary issue limiting the long-term success of the revascularization methods used to treat PAD. While atherectomy may help to mitigate or overcome some of the limitations of PTA, it is difficult to designate one revascularization method most effective for PAD given the nature of the disease.

A study by Quevedo et al. compared primary patency rates at 12 months in patients with infrainguinal arterial disease who were treated with balloon angioplasty and/or stenting alone with those who received atherectomy in addition to angioplasty/stenting.²³ Two randomized studies were obtained and served as

the basis of the analysis. When directional atherectomy was used as stand-alone treatment, primary patency at 12 months approached 60%. The primary patency at 12 months approached 90% when orbital atherectomy was used in conjunction with angioplasty and stenting. Despite the apparent synergies between atherectomy and PTA, authors concluded that there was insufficient data to justify use of atherectomy as stand-alone treatment in management of patients with PAD.

2. INVESTIGATIONAL DEVICE

2.1. Overview

The Rex Medical Revolution™ Peripheral Atherectomy System is intended for use in peripheral vessels of suitable patients with atherosclerotic PAD.

2.3. Model Numbers

The Revolution™ is available in the four different models, each with its own model number (**Table 1**).

Table 1. Revolution™ models

Model Number	Name	Length (cm)	Bit Size (mm)	Minimal RVD (mm)	Maximal RVD (mm)
2006145133	Revolution™	145	1.33	2.00	2.49
2006145166	Revolution™	145	1.66	2.50	2.99
2006145200	Revolution™	145	2.00	3.00	4.00
2006060133	Revolution™	60	1.33	2.00	2.49

RVD- Reference vessel diameter

2.4. Device Traceability

Lot number will be used to trace devices used in the study.

2.5. Intended Purpose of the Clinical Investigation

The purpose of this investigation is to evaluate the safety and effectiveness of the Revolution™ Peripheral Atherectomy System in the treatment of infrainguinal lower extremity peripheral arterial occlusive disease.

2.6. Indications for use

The Revolution™ Peripheral Atherectomy System is intended for use in atherectomy of the peripheral vasculature and to break apart and remove thrombus from the peripheral arteries inpatients with occlusive atherosclerotic disease.

2.7. Anticoagulation and antiplatelet therapy

The study device must not be used in subjects who cannot receive antiplatelet and in those who cannot receive systemic anticoagulant therapy.

The use of antiplatelet agents should be guided by the institutional standard of care. Subjects must receive aspirin at a dose of at least 80 mg per day, beginning at least one hour prior to the index procedure and continued through 6 months.^a

The subject must be systemically anticoagulated during use of the Revolution™ device. Adequate anticoagulation with unfractionated heparin or another standard agent must be administered prior to introduction of the study device. The level of systemic anticoagulation should be monitored per institutional guidelines, using, for instance, the activated coagulation time or another suitable measure, and should be maintained at adequate levels until withdrawal of the study device from the circulation.

2.8. Device Description

The Rex Medical Revolution™ Peripheral Atherectomy System is a minimally invasive catheter-based atherectomy system used to treat patients who suffer from PAD. This system is designed to treat a broad range of plaque types both above and below the knee and may address many of the limitations associated with existing treatment options.

The Revolution™ Peripheral Atherectomy System consists of a sterile, single-use handle containing an electric motor and circuitry (**Figures 1-6**, below). The handle is equipped with an on/off button and speed select switch. The speed select switch allows the user to engage a treatment speed of 140,000 rpm or a guidewire rapid exchange speed of 12,000 rpm. The rapid exchange (REX) setting breaks static friction, thereby facilitating exchange over the guidewire. The ablating mechanism consists of a spheroid-shaped burr coated in 15 µm diamond grit at the distal end of a flexible drive shaft. There are three (3) burr diameters: 1.33 mm, 1.66 mm, and 2.00 mm. The burr is rotated at 140,000 rpm to facilitate plaque ablation. The ablated plaque is brought into the catheter where it is mechanically conveyed from the patient using an Archimedes Screw fixed on the outer surface of the drive shaft. The drive shaft is equipped with a central lumen which accommodates a Rex Medical supplied 0.014" guidewire. The catheter uses coaxial construction to accommodate independent infusion and aspiration functions. The proximal end of the handle is composed of an adapter with two ports: one for debris

^a Discontinuation of antiplatelet therapy prior to 6 months for drug-related complications or for new or worsened medical conditions that increase antiplatelet agent-associated bleeding risk will not be considered to be a Protocol Deviation.

conveyance and the other for saline infusion. The system's power cable is designed to be plugged in to the supplied AC/DC converter which can be plugged into any standard 110V outlet.

The Revolution™ Peripheral Atherectomy System is designed for use with the silicone-coated Revolution™ Guidewire, also manufactured by Rex Medical. The Revolution™ Guidewire has a shaft diameter of 0.014" and is made of stainless steel with a smooth finish. The spring tip configuration is atraumatic, radiopaque, and malleable to allow formation of a steerable system. Also supplied is a Guide Wire Torquer, a plastic device that attaches to the guide wire to provide a gripping surface for guide wire manipulation.

The following items (supplied by Rex Medical) are required for proper use of the Revolution™ Peripheral Atherectomy System:

1. Revolution™ Peripheral Atherectomy System Handle (**Figure 1**)
2. Revolution™ Peripheral Atherectomy System Power Supply (**Figure 2**)
3. Disposal bag (500 mL) for material conveyed out of the aspiration port (**Figure 3**)
4. Saline bag spike and infusion tubing (**Figure 4**)
5. Rex Medical Revolution™ Guidewire (**Figure 5**)
6. Guidewire Torquer and Clip (**Figure 6**)

The operating room should be equipped with the following items:

1. Guide catheter/sheath introducer
2. Standard IV pole
3. Sterile heparinized (10,000 IU/L) 0.9% normal saline
4. Fluoroscopic imaging equipment
5. Standard 110 V electrical wall outlet
6. Other equipment as needed for interventional procedures

[figure not shown]

Figure 1. The Revolution™ Peripheral Atherectomy System Handle

[figure not shown]

Figure 2. The Revolution™ Peripheral Atherectomy System Power Supply

[figure not shown]

Figure 3. The Revolution™ Peripheral Atherectomy System Disposal

[figure not shown]

Figure 4. The Revolution™ Peripheral Atherectomy System Infusion Line

[figure not shown]

Figure 5. The Revolution™ Peripheral Atherectomy System Guidewire

[figure not shown]

Figure 6. The Revolution™ Peripheral Atherectomy System Guidewire Torquer and Clip

3. PRIOR INVESTIGATIONS

The Sponsor, Rex Medical L.P. (Conshohocken, PA), has developed the study device known as the Revolution™ Peripheral Atherectomy System. The Revolution™ Peripheral Atherectomy System has yet to be formally evaluated in the US. This clinical investigation will allow the Sponsor to collect safety and effectiveness data regarding its Revolution™ Peripheral Atherectomy System.

4. STUDY OBJECTIVES

The objective of this study is to evaluate the safety and effectiveness of the Revolution™ Peripheral Atherectomy System in the treatment of infrainguinal lower extremity peripheral arterial occlusive disease.

Safety will be evaluated by assessing freedom from 30-day Major Adverse Events (MAE), defined as the composite of all-cause mortality, clinically-driven target lesion revascularization (TLR), major target limb amputation, major target vessel perforation requiring surgical or endovascular repair and clinically-significant distal embolization in the target limb; as adjudicated by the independent Clinical Events Committee (CEC).

Effectiveness will be evaluated by acute debulking, assessed by technical success ($\leq 50\%$ diameter stenosis) after atherectomy with the study device, prior to adjunctive therapy with balloon angioplasty, stent deployment or other interventions. Effectiveness will be evaluated from post-atherectomy contrast angiograms, as evaluated by the independent core laboratory. Effectiveness will be assessed for all investigator-identified target lesions and calculated as the proportion of investigator-identified target lesions with technical success.

Secondary objectives will consist of the following:

- Change in percent stenosis after treatment with Revolution™ Peripheral Atherectomy System, determined after atherectomy and prior to other adjunctive therapies, as measured by the angiographic core laboratory;
- Procedural success as defined by target lesion residual stenosis of <30% at the conclusion of the index procedure, after atherectomy and any adjunctive endovascular treatment, as measured by the angiographic core laboratory;
- Assessment of the individual components of the primary safety endpoint (MAE); including all-cause mortality, major target limb amputation, clinically significant distal embolization, major target vessel perforation requiring surgical or endovascular repair, and clinically-driven TLR, measured through 30 days and at 6 months.;
- Minor unplanned amputation rate through 30 days and 6 months;
- Myocardial infarction through 30 days and 6 months;
- Incidence of target vessel revascularization (TVR) through 30 days and 6 months;
- Frequency of angiographic procedural distal embolization (symptomatic) in the target limb as confirmed angiographically by the core laboratory;
- Primary patency of the target lesion at 30 days and 6 months, determined by duplex ultrasound or angiography;
- Primary-assisted patency of the target lesion at 30 days and 6 months, determined by duplex ultrasound or angiography.
- Secondary patency of the target lesion at 30 days and 6 months, determined by duplex ultrasound or angiography.

5. OUTCOME VARIABLES

5.1. Primary Safety Endpoint Definition

The primary safety endpoint is a composite endpoint triggered by the occurrence of any of five categories of events through 30 days after the index procedure.^b These events are the following:

1. All-cause mortality- Death from any cause, from the point of enrollment through 30 days.
2. Clinically-driven TLR- Any revascularization of the target lesion that occurs after the subject has left the procedure room following the index procedure. TLR do not include adjunctive interventions performed during the index procedure, whether planned or for failed atherectomy or for complications of atherectomy. TLR are considered to be clinically-driven when they occur as a

^b The index procedure is considered to occur on day 0; the first post-procedure day is day 1, and so on. The 30-day time point includes any events with a start date prior to 11:59PM on day 30.

result of restenosis >50% diameter reduction as measured angiographically or by duplex ultrasound (occlusion or stenosis with Peak Systolic Velocity Ratio >2.4).^c

3. Perforation of the target vessel- Imaging evidence (standard contrast angiography, computed tomography angiography or open surgical/pathology visualization) of target vessel perforation from any cause. For angiography and CTA, perforation is defined by contrast extravasation outside of the adventitia.
4. Clinically-significant distal embolization- Target limb embolization documented on core laboratory-assessed angiography or with open surgery/pathology, accompanied by symptoms referable to the involved vascular bed.
5. Major amputation- Amputation of the target limb that results in limb shortening; i.e. is performed at or above the level of the malleoli.

5.2. Primary Effectiveness Endpoint Definition

The primary effectiveness endpoint is technical success defined as acute debulking resulting in a reduction of stenosis to $\leq 50\%$ after treatment with Revolution™ Peripheral Atherectomy System from baseline and prior to other adjunctive therapies at the conclusion of the index procedure, as measured by the angiographic core laboratory.

Within any target lesion, stenosis is measured at the point of the minimum luminal diameter (MLD) over its shoulder-to-shoulder length.^d The reference vessel diameter (RVD) is the interpolated diameter from the point just proximal to the point just distal to the target lesion. The percent stenosis is calculated as:

$$\% \text{ Diameter Stenosis} = 1 - \text{MLD/RVD}$$

6. STUDY DESIGN

The study population will include up to 121 subjects, male and female, who are appropriate candidates for endovascular treatment of infringuinal lower extremity peripheral arterial occlusive disease with the Revolution™ Peripheral Atherectomy System.

6.1. Study Design

This single-arm study of the Revolution™ Peripheral Atherectomy System includes subjects with PAD and significant target lesions of the appropriate diameter, located within the superficial femoral artery (SFA), popliteal and tibial arteries.

^c If an angiogram and a duplex ultrasound imaging study are discordant within any 30-day period, the angiographic results will supersede the duplex findings.

^d The shoulder-to-shoulder length is determined visually using a Quantitative Vascular Angiography (QVA) software application. RVD is determined at the location of the MLD, linearly interpolated between the luminal diameters just proximal to and distal to each shoulder.

6.2. Informed Consent

Written, study-specific Informed Consent will be obtained from each subject prior to treatment with the Revolution™ Peripheral Atherectomy System. The Investigator will keep the original Informed Consent Form and a copy will be given to the subject. It will also be explained to the subjects that they are free to refuse entry into the study and free to withdraw from the study at any time without prejudice to future treatment. Subjects will be consented for five years to allow for the ability to collect additional data, in the event that initial study results indicate a need for additional long-term information.

6.3. Inclusion Criteria

Subjects may be enrolled in the study if they meet the following criteria:

1. Age \geq 18 years;
2. Willing and able to provide informed consent;
3. Ability to take at least one form of anti-platelet therapy;
4. Rutherford categories 2, 3, or 4 in the target limb; Rutherford category 5 if no exposed bone, tendon or active infection;
5. Lesions to be treated with the study device must be located in the same limb;
6. Target lesion(s) located within the superficial femoral, popliteal or tibial arteries;
7. Target lesion(s) with stenosis $\geq 70\%$ diameter reduction as measured by site-reported angiography;
8. Target lesion length(s) ≤ 150 mm;
9. Target lesions(s) with reference vessel diameter (proximal and distal to target lesion) ≥ 2.0 mm and ≤ 4.0 mm.

A subject must have at least one target lesion that meets the anatomic inclusion criteria above. Other lesions that do not meet these criteria may be treated but must not be treated with the study device and will not be considered target lesions. Bilateral treatment with the study device is not permitted.

6.4. Exclusion Criteria

Subjects will be excluded from the study for:

1. Subjects in whom amputation above the ankle is necessary, irrespective of the success of revascularization;
2. In-stent restenosis within the target lesion;
3. Flow-limiting dissection, Type C or greater;
4. Target lesions within an autogenous or prosthetic bypass graft;
5. History of an endovascular procedure or open vascular reconstruction in the index limb within the last 30 days, including thrombolytic therapy;
6. Any open vascular surgical procedure planned in the target limb or endovascular procedures planned in the target vessel within 30 days after the index procedure;

7. Kidney disease of sufficient severity, in the Investigator's opinion, to contraindicate lower extremity angiography using standard or alternate contrast agents as per the local Standard of Care;
8. Pregnancy or breast feeding. A woman of child-bearing potential must have a negative pregnancy test within one week of index procedure;
9. Myocardial infarction or stroke within 2 months of enrollment;
10. Contraindication to antiplatelet, anticoagulant, or thrombolytic therapy;
11. Uncorrectable bleeding diathesis or platelet dysfunction or thrombocytopenia with platelet count <125,000/ μ L, known coagulopathy, or INR >1.5;
12. Known allergy to contrast agents or medications used to perform endovascular intervention that cannot be adequately pretreated in the opinion of the investigator;
13. History of heparin-induced thrombocytopenia;
14. Psychiatric disorder which, according to the investigator, has potential to interfere with provision of informed consent, completion of tests, therapy, or follow-up;
15. Clinical/angiographic evidence of distal embolization or acute thrombus;
16. Significant stenosis (>50% diameter reduction) or occlusion of inflow tract vessels that was not successfully treated (<50% residual stenosis without flow limiting dissection) before study intervention.

Treatment of iliac and common femoral artery lesions to gain access to a target lesion or to provide adequate inflow is permissible, but such inflow lesions must not be treated with the study device and will not be considered target lesions.

6.5. Study Populations

The point of enrollment in this study occurs when a study device first enters a subject's vasculature.^e The following populations will be analyzed in the study:

Intention to treat (ITT) analysis: The ITT analysis will be performed on all enrolled subjects in whom the study device entered the vasculature, irrespective of adherence with the entry criteria, treatment actually received, subsequent withdrawal, or deviation from the investigational plan.²⁴

Per Protocol analysis: The PP analysis will be performed on target lesions with core laboratory-determined RVD falling within the pre-specified anatomic eligibility criteria of ≤ 4.0 mm. The effectiveness endpoints will be determined using the PP analytic subset to exclude lesions where the largest bore (2.0 mm) study device is less than 50% of the RVD (see Section 7.3, page 22, below).^f

^e This point is defined as entry of the study device into the access sheath/guide at the level where the sheath/guide enters the subject's body.

^f Use of the 2.0 mm bore in a vessel larger than 4.0 mm in diameter would not result in a lumen channel that exceeds 50% of the RVD. In other words, the residual stenosis after successful atherectomy would still not meet the criteria

7. STATISTICS AND DATA ANALYSIS

7.1. Statistical Methodology

The objective of the statistical design for this study is to evaluate the safety and effectiveness of the study device, as assessed in comparison to literature-derived performance goals.

The safety and effectiveness performance goals were determined from a literature review of atherectomy publications. A total of 19 studies were included in this review and, among these, 13 reported data referable to the primary safety endpoint and 7 reported data referable to the primary effectiveness endpoint. Studies with populations that overlapped the population of another study were excluded.

7.2. Primary Safety Endpoint

The primary safety endpoint for this study is a composite endpoint of any MAE within 30 days, as adjudicated by the CEC. MAE is defined as 30-day all-cause mortality, clinically-driven TLR, major target limb amputation, major target vessel perforation requiring surgical or endovascular repair and clinically-significant distal embolization in the target limb. The rate of MAE will be compared to a performance goal with the following null and alternative hypotheses:

$$H_0: P_S \leq PG_S \text{ versus } H_A: P_S > PG_S$$

where P_S is the proportion of subjects free from MAE through 30 days and PG_S is the safety performance goal derived from the studies reporting the elements contained in the composite MAE endpoint.

The Exact binomial one-sided 97.5% confidence interval will be used to test the primary safety endpoint.

7.3. Primary Effectiveness Endpoint

The primary effectiveness endpoint is technical success, defined by $\leq 50\%$ diameter stenosis after atherectomy with the Revolution™ Peripheral Atherectomy System, prior to adjunctive therapy, as measured by the independent core laboratory on the post-atherectomy contrast angiogram. Effectiveness will be assessed for all investigator-identified target lesions in the PP analytic group and will be calculated on a per-lesion basis.

$$H_0: P_E \leq PG_E \text{ versus } H_A: P_E > PG_E$$

for technical success; even though the device performed as designed. Since the eligibility criteria are site-determined, the subject may still be included in the ITT population but the lesion would be excluded from the PP analytic group.

where P_E is the proportion of lesions with technical success, as defined by angiographically-determined $\leq 50\%$ target lesion diameter reduction on the post-atherectomy core laboratory measurement.^g The effectiveness performance goal, PGE, is technical success defined in the same manner, derived from the published literature.

The primary effectiveness endpoint will be calculated for those target lesions that fall at or below the specified acceptable reference vessel diameter of 4.0 mm, as determined by the core laboratory. Target vessels with diameters > 4.0 mm will be excluded from the analysis, since even the largest bit size (2 mm) would not result in a post-atherectomy channel size of $\geq 50\%$ RVD.

The primary effectiveness endpoint analysis will use the E+M approach for one sample correlated binary data with cluster size of one or two that accounts for correlations between multiple target lesions within the same subject.^h

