Analytical Sets	The regulatory submission will be based on an approximate sample size of 121 subjects. Assuming a lesion-to-subject ratio of 1.5, approximately 165 target lesions will be evaluable for the primary effectiveness endpoint. Subset analyses will be performed for device effectiveness for superficial femoral/popliteal and tibial artery target lesions.
Pre-Enrollment Testing	Medical history, physical examination with vital signs and directed peripheral vascular examination, laboratory assessment, ankle-brachial or toe-brachial index, and patient-reported outcome measures. The diagnostic angiogram at time of the planned index procedure is performed prior to the point of enrollment in the study; eligibility is, in part, based upon the anatomic findings of the angiogram.
Follow-Up Schedule	Subjects will have required follow-up evaluations at the following time points: 
1. Discharge;2. 1 month post index procedure;3. 6 months post index procedure;
Follow-Up Data Collection	
1. Adverse Events at the index procedure, hospital discharge, and through 6 months;2. Rutherford Category at 1 and 6 months;3. Ankle-brachial or toe-brachial index at 1 and 6 months;4. Duplex ultrasound or angiography of the target vessel at 1 and 6 months.
Clinical Events Committee (CEC)	An independent CEC will review all primary safety endpoint events, unanticipated adverse device effects, and other important safety occurrences as specified in the CEC Charter.
Data Safety Monitoring Board (DSMB)	An independent Data Safety Monitoring Board (DSMB) will review safety data from the study at predetermined time points and as deemed necessary by the Sponsor or the DSMB Chair. The DSMB will make recommendations on protocol modifications and continuation of the study.
Principal Investigator	[name], MD

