7.9. Sample Size

The PG of 80% has been established for the primary safety endpoint, based on a one-sided 97.5% exact binomial test. The 30-day MAE rate is anticipated to be approximately 9%. Under these assumptions, the required sample size to achieve a level of 90% power is 110 subjects (**Table 4**). Assuming 10% attrition over 30 days, initial enrollment of 121 subjects is necessary.

A PG of 76% has been established for the primary effectiveness endpoint. Anticipating an actual technical success rate of approximately 86%, and based upon a one-sided 97.5% exact binomial test, the required sample size to achieve a level of 90% power is 165 target lesions. Assuming a 1.5 ratio of subjects to treated target lesions, approximately 110 subjects will be necessary (**Table 5**). Since the primary effectiveness endpoint is determined at the time of the index procedure, no attrition has been taken into account.

ⁱ The TALON publication reported the results in 1258 target lesions, among which 132 required preliminary balloon dilatation to deliver the device and technical success ($\leq 50\%$ residual stenosis after atherectomy) was not achieved in 54 lesions. Technical success was calculated assuming there was no overlap between these cases; i.e. technical success was achieved in 1072 (1258 – 132 - 54) lesions.

Table 4. Sample Size – Primary Safety Endpoint

Primary Safety Endpoint	
Performance goal	80%
Anticipated freedom from MAE	91%
Significance level	.025
Statistical test	One-sided exact binomial test
Desired power level	90%
Required sample size prior to 10% 30-day attrition rate	110
Required sample size after attrition adjustment	121

Table 5. Sample Size – Primary Effectiveness Endpoint

Primary Effectiveness Endpoint	
Performance Goal	76%
Anticipated technical success rate	86%
Significance level	.025
Statistical test	One-sided exact binomial test
Desired power level	90%
Required sample size (target lesions)	165
Estimated subjects required for required number target lesions*	110

* Assumes 1.5 target lesions treated per subject; a ratio calculated from the studies in the atherectomy literature review

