8.2. Point of Enrollment

Subjects will be consented prior to the index procedure, at a point where the anatomic eligibility criteria may be unknown to the Investigator. Enrollment in the study will occur at the point of insertion of the study device into the vasculature, when the device enters the portion of the sheath/guide that resides within the subject's arterial tree.

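### No rule fixes the target-lesion list before the device is used or scores a lesion the device cannot reach, so technical success can be biased upward, mainly through second or later lesions

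*Protocol*

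**What the plan says.** **Denominator.** Protocol 7.3: "Effectiveness will be assessed for all investigator-identified target lesions in the PP analytic group and will be calculated on a per-lesion basis". Protocol 4 and SAP 1.2 also refer to lesions identified by the investigator. Protocol 6.5 and SAP 3.2 define the per-protocol (PP) set by a core-laboratory reference vessel diameter (RVD) of at most 4.0 mm. Failed delivery is not a ground for exclusion.

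**What may be a target.** Protocol 6.3 sets site-read limits on location, stenosis, length and diameter, and requires at least one qualifying lesion. Lesions that fail those limits "must not be treated with the study device and will not be considered target lesions".

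**Timing.** The synopsis (Pre-Enrollment Testing) places the diagnostic angiogram before enrollment and says that "eligibility is, in part, based upon the anatomic findings of the angiogram". Under Protocol 8.2, consent is taken "at a point where the anatomic eligibility criteria may be unknown to the Investigator", and the subject is enrolled when the device enters the vasculature. Table 6 places eligibility verification at screening only. Its Treatment column holds only adverse event assessment. The Treatment form items in 8.3 include neither target-lesion identification nor the angiogram taken after atherectomy and before adjunctive therapy.

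**Missing values.** Under Protocol 7.6 and SAP 4.7, a target lesion without a minimum luminal diameter (MLD) after atherectomy is treated as missing at random and imputed by random draw from measured lesions. A tipping-point analysis follows.

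**Size.** Protocol 7.9: "A PG of 76% has been established for the primary effectiveness endpoint", and "the required sample size to achieve a level of 90% power is 165 target lesions". This assumes 86% true success and 1.5 lesions per subject.

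**The concern.** The endpoint is a proportion of lesions, so its denominator has to be settled before the outcome is visible. In this single-arm study the operator both names the lesions and sees the result. The plan locks the subject but not the lesion.

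Take a subject with two qualifying lesions, where the device treats the first and cannot be delivered to the second. Two things can happen:

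- The second lesion is never recorded as a target and so is not counted. The anatomic criteria say which lesions may be targets. They do not say that every qualifying lesion must be declared.
- It is recorded but has no post-atherectomy measurement. Imputation then draws its result from lesions that the device did reach.

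Both routes turn a device failure into something better than a failure. No misconduct is needed: with no stated time, sites can reasonably differ on whether an unreached lesion was ever a target. The imputation and tipping-point rules cannot repair the first route, because they act only on declared lesions.

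**Working it through.** **Inputs.** From Protocol 7.9: goal 76%, anticipated success 86%, one-sided alpha 0.025, exact binomial test, 165 lesions, 1.5 lesions per subject. From Protocol 7.4: success requires a lower confidence limit (LCL) above 76%. Assumed, because the documents give no figure: the share of intended lesions dropped (3% or 5%), that all dropped lesions are failures, and that lesions are independent.

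**The plan's own figure.** The normal approximation gives

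n = [(1.960·√(0.76·0.24) + 1.2816·√(0.86·0.14)) / 0.10]² = 164.3, rounded up to 165.

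This matches the plan. The exact test at n = 165 passes with 137 or more successes; its true alpha is 1.9% and its power 88.5%. The smallest n with exact power of at least 90% is 167.

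**Lesions at risk.** 110 subjects × 1.5 = 165 lesions, so 165 − 110 = 55, one third, are second or later lesions.

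**Route 1, lesion undeclared.** Let true success over all intended lesions be 76%, the null value. If a share d is dropped and all are failures, apparent success is 0.76/(1 − d).

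| Dropped | Lesions analysed | Apparent success | Successes needed | Chance of passing |
|---|---|---|---|---|
| 0% | 165 | 76.0% | 137 | 1.9% |
| 3% | 160 | 78.4% | 133 | 8.2% |
| 5% | 157 | 80.0% | 131 | 16.4% |

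The fair comparator is the exact 1.9%, not the nominal 2.5%. If the number dropped varies at random around 5% instead of being fixed at 8, the last figure is 18.6%.

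**One dataset.** 133/165 = 80.6%, LCL 73.7%: fails. With five unreached lesions left out, 133/160 = 83.1%, LCL 76.4%: passes.

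**Route 2, lesion declared but imputed.** Keep the same five lesions in the denominator and draw their results from the 160 measured ones. The expected number of successes is 133 + 5 × 133/160 = 137.2 of 165, against 137 needed. The point estimate is again 83.1%. Between-imputation variance would widen the interval somewhat, but the bias has the same direction and about the same size.

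**How the goal was built.** Protocol 7.3 says the goal uses the same definition of technical success. Table 3 totals 89 + 123 + 164 + 131 + 86 + 1258 + 164 = 2015 lesions, of which 1258 come from one registry. Footnote i removes that registry's 132 lesions that needed balloon pre-dilatation for delivery from the successes but keeps them in the denominator: 1258 − 132 − 54 = 1072, and 1072/1258 = 85.2%. Leaving them out of the denominator would have given 1072/1126 = 95.2%. The goal's largest source therefore charged delivery difficulty to the device, and the trial's rules need not.

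**The case against.** The strongest reply is that the choice of lesions is far from free, and much of it stands. Targets must meet four site-read anatomic limits. Protocol 8.1 asks for lesion characterization at screening, and Table 6 asks for duplex or angiography within 90 days. The diagnostic angiogram precedes enrollment, and at least one qualifying lesion is required. So one lesion per subject is in effect identified before the device enters, and the exposure lies mainly in the 55 or so additional lesions. Dropping 8 of those would be about 15% of them, every one a failure: a scenario, not an estimate. The electronic forms and the Core Lab Manual, which are not among the documents, may also record lesions in advance.

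A reader might infer three stronger things that the documents do not support:

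- *That Protocol 6.3 makes any lesion treated by other means non-target.* It does so only for lesions that fail the anatomic criteria. A qualifying lesion ballooned after failed delivery is not reclassified by that sentence.
- *That anatomy is known only from the index angiogram.* Baseline imaging exists, and 8.2 says only that anatomic eligibility may be unknown at consent.
- *That selection could never be detected.* The Treatment form records device passes and issues, adjunctive therapy and additional procedures. Protocol-specified imaging goes to the core laboratory (13.6), and monitors check source records. A failed delivery would usually leave a trail.

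None of this supplies the missing rule. A trail lets someone suspect that a lesion was intended; it does not say whether that lesion belongs in the denominator or how it scores.

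**Conclusion.** The gap is real but narrower than free choice of lesions by the operator. Two rules are missing: when the list of target lesions is fixed, and how an unreached lesion is scored. The first lets a second or later qualifying lesion go undeclared. The second sends a declared lesion without a post-atherectomy MLD to imputation from lesions the device did reach. Both bias technical success upward and depart from how the largest source of the performance goal was counted.

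Five lesions out of 165 can reverse the primary conclusion. At a true rate equal to the goal, the chance of passing rises from 1.9% to about 8% with 3% dropped and about 16% with 5% dropped. These figures rest on an assumed dropped share, on every dropped lesion being a failure, and on independent lesions. Within-subject correlation, which SAP 4.3 handles by generalized estimating equations, would change them. The tipping-point analysis would show sensitivity to declared but unmeasured lesions; it does not change the primary result and cannot see undeclared ones. This should be fixed before enrollment, because intent is hard to reconstruct afterwards.

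**What to change.** 1. **Protocol 8.2, 8.3 and the Treatment column of Table 6.** After the diagnostic angiogram and before the device enters the sheath, the site records each intended target lesion (vessel, segment, length, diameter) with a time stamp and sends the list to the core laboratory.
2. **Protocol 7.3 and SAP 4.3.** Define the denominator as all listed lesions in enrolled subjects that meet the core-laboratory RVD rule, whether or not the device reached them.
3. **Protocol 7.6 and SAP 4.7.** Count a listed lesion where the device was attempted but not delivered as a technical failure. Limit imputation to lesions that were treated but lack a readable post-atherectomy image. Without this step the list alone would achieve little, since imputation would restore most of the inflation. State also how a listed lesion in which the device was never tried is scored.
4. **Table 6.** List the post-atherectomy, pre-adjunct angiogram of each listed lesion as a required Treatment assessment, so that its omission is a deviation.

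The cost is one form page and some wording. No procedure is added, because the endpoint already depends on these angiograms. The success rate will be slightly less favourable. If 86% is the rate over all intended lesions, planned power is unchanged. If it is the rate among reached lesions only, exact power at 165 falls from 88.5% to about 81%, 71% or 60% with 1%, 2% or 3% unreached. The sponsor should state which rate is meant.
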